### **How Research will be Introduced to Participants**

At the pre-operative surgical visit, eligible patients will be introduced to the research by the surgical team. Approximately 1 week prior to the surgery, a member of the research team will call the patient to discuss the study further and address any additional questions or concerns. They will also discuss the study in detail, confirm understanding, and review the consent form with the patient.

### **How Participants will be Screened**

At the pre-operative surgical clinic visit, patients will be screened for eligibility based on stated inclusion and exclusion criteria. The patient will be screened again during the follow-up phone call made by a member of the research team approximately one week before the scheduled surgery.

### **Risk to Subjects**

Complications for TAP blocks and its variants, including the subcostal TAP block, are rare. Incorrect needle advancement through the peritoneum may result in injuries to organs such as to the stomach or bowel perforation. Other complications include hematoma, infection and local anesthetic toxicity.

### **Description of Procedures Taken to Lessen the Probability or Magnitude of Risks**

To minimize risk, ultrasound guidance will be used for all subcostal TAP blocks. Slow injection of local anesthetic with intermittent aspiration will help reduce the risk of inadvertent vascular injection of local anesthetic. Patients will be monitored in accordance to the standards of the American Society of Anesthesiologists during the entirety of the surgery. Following the surgery, they will be monitored in the post-anesthesia care unit.

### **Provisions for Research Related Harm/Injury**

Patients will be provided with a phone number to call for any concerns related to surgery, anesthesia or the study. Should any complication requiring medical attention arise, patients will be instructed to return to the hospital. Subjects injured as a result of this study will be treated, with the costs billed to them and/or their insurance company. Patients will not be compensated for research related injury.

### **Expected Direct Benefit to Subjects**

Patients who receive a subcostal TAP block may experience less postoperative pain. This may possibly lead to lower opioid consumption, and thereby, result in fewer side effects related to opioid consumption.

### **Benefit to Society**

Subcostal TAP blocks may be incorporated into an Enhanced Recovery after Surgery protocol for laparoscopic gastrectomies should this study show decreased opioid consumption and improved outcomes with this truncal nerve block.

### **Provisions to Protect the Privacy Interests of Subjects**

De-identified data will be stored on secure, password-protected servers maintained by the Mount Sinai Information Technology department. Access to the data will only be available to Mount Sinai IT administrators and the study investigators. A one-way hash ID will be generated for each record once the de-identified data set is released for analysis. Only the study investigators with access to the full data set will be able to match the hash ID to the original record. All investigators must have completed the HIPAA training pertaining to PHI confidentiality.

### **Economic Impact on Subjects**

There is no additional cost to subjects for participating in this study. There is no compensation for participants.

### **Description of Study Design**

Patients who are eligible for this subject will be invited to participate. Written informed consent will be obtained from eligible volunteers for this study.

This study will be a double-blinded randomized control trial. Patients will be randomized into one of two groups. Patients in Group 1 will undergo general anesthesia with a post-induction, post-intubation, pre-procedural subcostal TAP block with 40 mL 0.25% bupivacaine on the ipsilateral side as the extraction site. Patients in Group 2 will undergo general anesthesia with a post-induction, post-intubation, pre-procedural subcostal TAP block with 40 mL sterile normal saline on the ipsilateral side as the extraction site. Investigators will be blinded to the randomization of these patients. Following performance of these blocks, patients will receive standard care for the surgery as well as during the postoperative recovery period. Data will be obtained from the EPIC electronic medical record, and from the anesthesia computer record. Patients will be asked postoperatively to assess items such as their nausea and pain scores. Patients will also be contacted by phone within 1-2 days of discharge to obtain analgesic satisfaction scores. This data will be collected on the Redcap server.

### **Description of Procedures being Performed**

Group allocation and instructions on preparing the injectate solution for the subcostal TAP block will be included in a sealed envelope. On the day of the surgery, the group allocation will be

revealed to an anesthesiologist not involved with the research study. The anesthesiologist will prepare the solution to be used for the subcostal TAP block.

Standard ASA monitors will be applied to all patients. A preoperative intravenous line will be placed. Patients will undergo standard induction with IV propofol, fentanyl and rocuronium. All study patients will receive 1.5mcg/kg of IV fentanyl on induction. Following induction, a subcostal TAP block will be performed on the ipsilateral site as the extraction site. Patients will be positioned in the supine position. A linear ultrasound probe will be parallel to the lower margin of the rib cage. The rectus abdominis muscle, posterior rectus sheath, and transversus abdominis muscle are identified on the ultrasound. A block needle will be advanced using an in-plane approach from medial to lateral, targeting the fascial plane between the posterior rectus sheath and the transversus abdominis muscle. For group 1 patients, 40mL of 0.25% bupivacaine will be deposited in this fascial plane. For group 2 patients, 40mL of normal sterile saline will be used instead.

General anesthesia will be maintained with inhalational anesthetic gas. Boluses of fentanyl will be given to all patients for pain control as needed, regardless of which group they are assigned to. Patients will also receive muscle relaxants for surgical relaxation as needed. Standard intravenous antiemetics, 8mg ondansetron and 10mg dexamethasone, will be given at the end of the surgery prior to extubation, unless otherwise contraindicated. Surgeons will use local anesthetic to subcutaneously infiltrate the other port sites. Following extubation, patients will recover in the post-anesthesia care unit (PACU) and then to the general hospital floor. Patients will be given scheduled intravenous acetaminophen 1000 mg and ketorolac (30 mg), as well as PRN intravenous opioids, i.e. fentanyl, hydromorphone.

#### **Description of the Source Records that Will be Used to Collect Data about Subjects**

Data will be collected from computerized medical record charts including EPIC and Compurecords. Investigators will also ask subjects questions about items such as their pain, nausea, and satisfaction with analgesia care.

#### **Description of Data that Will be Collected Including Long-Term Follow-Up**

Data collected includes age, gender, BMI, ASA status, duration of surgery, total opioid use in PACU, total opioid consumption in 24 hours, severity of pain at rest on a Likert scale (0-10) and presence of postoperative nausea (yes/no) at 1 hour, 6 hours, 12 hours and 24 hours postoperatively, time to breakthrough pain after surgery, area of pain after surgery, time to ambulation after surgery, analgesia satisfaction score at time of discharge, and hospital length of stay.

#### **Where and When Consent will be Obtained**

Verbal consent will be obtained via telephone approximately 1-2 weeks prior to the surgery. Written consent will be obtained on the day of the surgery.

#### **Waiting Period for Obtaining Consent**

Patients will receive a written consent form to review at the time that their surgery is scheduled. Approximately 1-2 weeks prior to surgery, the patient will be contacted by an investigator to discuss the study in detail, answer all questions and confirm understanding. Subjects will provide verbal consent for the study via this telephone call. On the day of surgery, they will sign a written consent form.

### **Description of Health Information that will be Viewed, Recorded or Generated**

The following data will be collected:

1. Amount of intraoperative IV opioid consumption
2. Amount of post-operative IV opioid consumption
3. Severity of pain at rest using an 11-point numeric pain score Likert scale at 1, 6, 12 and 24-hour marks postoperatively
4. Time to breakthrough pain after surgery
5. Area of pain after surgery
6. Presence of postoperative nausea (yes/no) at 1, 6, 12 and 24-hour marks postoperatively
7. Time to ambulation after surgery
8. Analgesia satisfaction score at time of discharge
9. Hospital length of stay

### **How PHI will be Protected from Improper Use or Disclosure**

Only study investigators will have access to patient data. All research team members must have completed the institutional HIPAA certification. Extracted data will be stored on the Mount Sinai Redcap data server, which is stored in accordance to Mount Sinai research policies. A one-way hash ID will be generated for each record in order to de-identify the subjects. Only study investigators with access to the full data set will be able to match the hash ID to the original source. De-identified data will be given to a statistician employed by the Mount Sinai Department of Anesthesiology for analysis.

### **When and How PHI will be Destroyed**

Following publication of this study, PHI will be destroyed. Digital encrypted files on the Mount Sinai network will be deleted permanently.

### **Description of PHI that will be Shared**

Age, sex, BMI, ASA status will be shared. All other subject demographics such as name, MRN or date of birth will not be shared.

### **Justification for Sharing PHI**

De-identified data will be given to a statistician employed by Mount Sinai Department of Anesthesiology for data analysis.

### **With Whom Directly PHI will be Shared**

De-identified data will be given to a statistician employed by Mount Sinai Department of Anesthesiology for data analysis.

**Location where Data will be Stored**

Extracted data will be stored on the Mount Sinai Redcap data server, which is stored in accordance to Mount Sinai research policies.

**Duration Data will be Stored**

Data will be stored for the duration of the study until publication. Following publication, the data will be deleted permanently from the Mount Sinai network.

**Steps that will be Taken to Secure the Data during Storage Use and Transmission**

Encrypted and secured flash drives and Mount Sinai emails will be used for data transmission. All study data will be stored electronically in accordance to Mount Sinai Hospital policies.

**Data analysis plan including any statistical procedures**

Data analysis will be completed by a biostatistician employed by the Department of Anesthesiology.

## Summary of Study Design

- Inclusion Criteria:
  - Adults 18-80 years old
  - Body mass index >27 and <45 kg/m^2
  - Candidate for general anesthesia
  - Undergoing laparoscopic sleeve gastrectomy
  - Patients of participating surgeons
- Exclusion Criteria:
  - Prior bariatric surgery of any kind
  - Previous abdominoplasty
  - Allergy or intolerance to one of the study medications
  - ASA ≥ 4
  - Chronic opioid use (taking opioids for longer than 3 months or daily oral morphine equivalent of >5mg/day for one month)
  - History of alcohol/drug abuse
  - History of hepatic or renal insufficiency
  - Patient refusal
  - Patients who do not speak English
- Eligible patients identified during surgery clinic → Phone call 1-2 weeks prior to surgery to discuss study, assess participation, and obtain verbal consent → Written consent obtained on day of surgery
- Group allocation information revealed to separate anesthesiologist on the day of surgery
- Intraoperative Management
  - Induction: propofol, rocuronium, lidocaine, 1.5mcg/kg fentanyl
  - Ipsilateral subcostal TAP block performed
  - Maintenance: sevoflurane, rocuronium as needed, fentanyl as needed
  - Prior to extubation: 8mg ondansetron and 10mg dexamethasone unless otherwise contraindicated
  - Surgeon will infiltrate other port sites with local anesthetic subcutaneously
- Following extubation, patients will receive opioids along with scheduled IV acetaminophen and ketorolac unless otherwise contraindicated
- Investigator or nurse will assess:
  - Pain at rest using 11-point numeric pain score Likert scale at 1, 6, 12 and 24-hour marks postoperatively
  - Presence of postoperative nausea (yes/no) at 1, 6, 12 and 24-hour marks postoperatively
  - Area of most pain after surgery (assessed on postoperative day 1)

- Analgesia satisfaction score at time of discharge (assessed via telephone call within 1-2 days of discharge)
- Data from EPIC
  - Amount of post-operative IV opioid consumption
  - Time to breakthrough pain (time from surgery end to first requirement of IV opioid)
  - Time to ambulation after surgery
  - Hospital length of stay
- Data from Compurecord
  - Amount of intraoperative IV opioid consumption

Effect of Unilateral Ultrasound-Guided Subcostal Transversus Abdominis Plane Block in Patients Undergoing Laparoscopic Sleeve Gastrectomy

PI: [name]
NCT03856788
Document Date: Aug 24, 2022

Statistical Analysis Plan

Baseline descriptive statistics will be performed for demographic variables, intraoperative data, and for potential confounders. All variables will be checked for normality via Kolmogorov–Smirnov test or Shapiro–Wilk test as well as histogram visual inspection. Normal variables will be reported as mean, standard deviation, non normal variables will be reported as median [IQR]. Proportions will be reported as n(%) and analyzed via Chi Square test. Normal continuous variables will be analyzed via t test, or paired t-test depending on the variable. Non-normal variables will be tested via Mann-Whitney U test. Area-under the curve analyses will be evaluated through ROC analysis or other tests as indicated. Where applicable, linear or logistic regression will be utilized to assess for associations of variables for both univariate and multivariate analysis.

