### **Objectives**

Primary Objective:

Compare amount of intravenous (IV) opioid consumption within 24-hour period amongst laparoscopic sleeve gastrectomy patients who receive the unilateral ultrasound-guided subcostal TAP block with bupivacaine to those who receive the block with only sterile saline.

Secondary Objectives:

- a. Amount of intraoperative IV opioid consumption
- b. Amount of post-operative IV opioid consumption
- c. Severity of pain at rest using an 11-point numeric pain score Likert scale at 1, 6, 12 and 24-hour marks postoperatively
- d. Time to breakthrough pain after surgery
- e. Area of pain after surgery
- f. Presence of postoperative nausea (yes/no) at 1, 6, 12 and 24-hour marks postoperatively
- g. Time to ambulation after surgery
- h. Analgesia satisfaction score at end of hospital stay
- i. Hospital length of stay

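### A normality check on the trial's own outcome data picks the primary test, and no between-arm estimate or confidence interval is specified

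*SAP*

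**What the plan says.** The Protocol, under Objectives, sets the primary objective: "Compare amount of intravenous (IV) opioid consumption within 24-hour period", bupivacaine block against saline block. Its section on the data analysis plan says only who will do the work: "Data analysis will be completed by a biostatistician employed by the Department of Anesthesiology".

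The method is therefore all in the SAP's one paragraph. It does not name the primary outcome, which is reached only through the opening words of this sentence: "All variables will be checked for normality via Kolmogorov–Smirnov test or Shapiro–Wilk test as well as histogram visual inspection". The result sets the summary (mean and SD, or median and IQR) and the test:

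- If the data pass the check: "Normal continuous variables will be analyzed via t test, or paired t-test depending on the variable".
- If the data fail the check, a rank test applies instead: "Non-normal variables will be tested via Mann-Whitney U test".

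Modelling is left open: "Where applicable, linear or logistic regression will be utilized to assess for associations of variables for both univariate and multivariate analysis". No covariates are listed and the model has no stated role for the primary outcome.

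Neither document states:

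- which of the two formal checks governs, or its threshold;
- whether Kolmogorov–Smirnov (K-S) is corrected for an estimated mean and SD;
- whether arms are checked separately or pooled;
- what happens when the check and the histogram disagree;
- a between-arm effect measure or confidence interval;
- alpha or sidedness.

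**The concern.** A primary analysis should be identifiable before outcome data are seen. Here two analysts could follow the paragraph faithfully and run different primary tests on the same data. The *or* between the two checks matters because they differ greatly in sensitivity to skewness. As-needed opioid totals cannot be negative and are plausibly skewed. The histogram adds a judgement with no rule attached.

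Two things are at stake. First, in some trials the t test and Mann-Whitney fall on opposite sides of 0.05, so an unstated choice settles the verdict. Second, the trial could end with a p-value and two arm summaries but no effect size with its uncertainty, which is what a reader needs to judge whether the block saves a worthwhile amount of opioid.

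**Working it through.** **Inputs.** The documents supply the outcome, two randomised groups and the selection rule. They give no sample size, SD, effect, alpha or power, so there is no stated figure to reproduce and everything below is assumed:

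- Data: gamma, shape 2, scale 1. Mean 2, SD √2 = 1.414, skewness 2/√2 = 1.41.
- Effects: a shift of 0.5 SD = 0.707, or a 30% proportional reduction, 0.3 × 2 = 0.600 in the mean (0.600/1.414 = 0.42 SD).
- Sample size: 30, 40 or 50 per arm, 6,000 simulated trials per cell.
- Tests: Welch t test and asymptotic Mann-Whitney, two-sided 0.05. Each arm is checked at 0.05, and data count as non-normal if either arm fails.

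**Step 1: which test is selected (30–50 per arm).**

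| Check | Sent to Mann-Whitney |
|---|---|
| Shapiro–Wilk | 93.3–99.8% |
| K-S, corrected | 70.0–91.4% |
| K-S, uncorrected | 4.5–15.9% |

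Uncorrected K-S used alone thus sends 100 − 15.9 = 84.1% to 100 − 4.5 = 95.5% of trials to the t test.

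**Step 2: how often the two tests disagree at 0.05 (30/40/50 per arm).** Shift 14.4/15.2/15.5%; proportional 12.0/12.2/12.4%. Repeat runs at 40 per arm spread up to about 17%.

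**Step 3: how often the choice of check changes the verdict.** This needs both the checks and the tests to disagree, so it cannot exceed the step 2 figure.

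| Shapiro–Wilk route against (30/40/50 per arm) | Shift | Proportional |
|---|---|---|
| K-S, corrected | 2.0/1.3/0.7% | 2.7/1.7/0.8% |
| K-S, uncorrected | 12.8/12.8/12.2% | 10.7/10.6/10.0% |

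Plausibility check: Shapiro–Wilk and uncorrected K-S disagree on normality in 84.0–89.8% of trials. At 40 per arm under a shift, 15.2% × 0.840 = 12.8% and 15.2% × 0.898 = 13.6%, in line with the simulated 12.8%. Repeat runs at 40 per arm gave about 11–14%.

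**Step 4: let the histogram count.** The SAP requires it, so uncorrected K-S alone is not quite the stated rule. As an assumed proxy, call data non-normal if uncorrected K-S rejects or either arm's sample skewness passes a cut-off (40 per arm, 2,500 trials per cell; shift/proportional).

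| Rule | Sent to t test | Verdict differs from Shapiro–Wilk route |
|---|---|---|
| Uncorrected K-S alone | 91/90% | 13.0/10.6% |
| Plus skewness > 1.0 | 19/18% | 2.3/2.4% |
| Plus skewness > 0.75 | 5/5% | 0.4/0.7% |

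**Step 5: type I error.** Following one check, per arm or pooled, gives 4.7–5.8% across all cells. If the analyst could take whichever test was significant, it would be about 6.6%.

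**Step 6: power at 40 per arm** (Shapiro–Wilk / corrected K-S / uncorrected K-S routes). Shift 74/73/63%; proportional 55/56/61%. A smaller repeat run put the proportional figures 3–4 points lower, with a similar gap between routes. Neither test is better for both kinds of effect.

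**Sensitivity to distribution.** With a real effect, the t test and Mann-Whitney disagreed in 4–8% of trials with normal data, about 10% with gamma shape 4 (20 per arm) and 9–17% with lognormal data (20–50 per arm).

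**The case against.** The strongest reply is that choosing a test by a normality check is common, either test is valid in a randomised comparison, and the practical effect is small. Much of that stands. Step 5 shows no type I error problem when one check is followed, and an unadjusted randomised comparison is not biased. With corrected K-S, or a histogram that can overrule an insensitive K-S, the verdict rarely changes. Custom does not, however, supply the missing rule or the missing estimate, and optional regression with no assigned role does not fill the gap.

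A reader might infer more than the documents support in four ways:

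- *That 10–14% is the expected effect.* It is a worst case: uncorrected K-S with no histogram override. The SAP calls for the histogram too. Because it gives no rule for disagreement, the worst case is possible but not to be presumed.
- *That the reported effect would be distorted.* Under the proportional model the difference in medians is 0.3 × 1.678 = 0.503 against 0.600 in means, 16% smaller. But the SAP attaches means and medians to the reporting of variables and promises no between-arm estimate of either kind. The accurate criticism is that none is specified.
- *That the favourable test will be picked.* The 6.6% figure needs deliberate selection, and nothing in the documents indicates that.
- *That outcome data shaped this SAP.* The Protocol is dated September 2019 and the SAP August 2022, but neither says whether unblinded data had been seen.

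**Conclusion.** The concern holds as a gap in specification. The only analysis text lets a check on the trial's own outcome data choose the primary test, with no tie-break, and no between-arm effect or confidence interval is fixed. That conclusion rests on the text and needs no simulation.

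The size is illustrative, resting on gamma shape 2 data, 40 per arm, a 0.5 SD shift or 30% reduction, and tests at 0.05. The two tests disagree in about 12–17% of trials. The unstated choice of check changes the verdict in about 1–3% under corrected K-S or a histogram override (the lowest proxy result was 0.4%), and in up to about 10–14% at worst. Less skewed data would give less disagreement between the tests. The histogram proxy is itself an assumption. The case for change rests on the missing primary analysis and estimate, not on the worst-case percentage.

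**What to change.** Delete the normality-based choice for the primary outcome and name one analysis in advance. State one opioid-equivalent unit and its conversion: the Protocol's procedures section allows both fentanyl and hydromorphone and gives no conversion. Report a between-arm estimate with a 95% CI.

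One suitable choice is linear regression of 24-hour IV opioid consumption on arm with robust (HC2) standard errors. It may be adjusted for baseline age, gender and BMI, which are already recorded ("Data collected includes age, gender, BMI, ASA status, duration of surgery"). Add Mann-Whitney with a Hodges-Lehmann difference and 95% CI as a fixed sensitivity analysis, whatever the distribution looks like. Making Mann-Whitney with Hodges-Lehmann primary would cure the defect equally well. Adjustment is optional, not the correction of a bias. If unblinded outcome data have already been seen, disclose that timing.

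The cost is SAP wording, the conversion and a little programming. The power trade-off at 40 per arm depends on covariate R², which the documents do not give:

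- **Shift:** adjusted regression 60/62/64/68/76% at R² 0/0.05/0.1/0.2/0.3, against 73–76% for Mann-Whitney, with skewed covariates. With two normal covariates and one binary, it was 62% v 70% at R² 0.1, 69% v 68% at 0.2 and 73% v 64% at 0.3. Regression therefore has less power unless R² reaches roughly 0.2–0.3.
- **Proportional reduction:** adjusted regression 57/58/61/67/70%, against 52–54%, so regression has more.
- **If R² is 0:** adjustment costs about 1–2 power points against unadjusted regression and widens the interval by about 2% (width ratio 1.019).
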